Heart Rate Response to Regadenoson and Sudden Cardiac Death

Study Protocol & Statistical Analysis Plan

NCT01842035

January 14, 2021

[name] Principal Investigator
University of Alabama at Birmingham
Birmingham, AL 35294

Heart rate response to regadenoson and sudden cardiac death

Objectives:

The main objectives of this proposal are to investigate whether:

1. A blunted heart rate response to regadenoson is an independent predictor of sudden cardiac death.
2. A blunted heart rate response to regadenoson can be used as a predictor of response to implanted cardiac defibrillator (ICD) on top of traditionally used indicators.

Hypotheses:

1. Patients with a blunted heart rate response to regadenoson are at higher risk of sudden cardiac death (death or appropriate cardiac defibrillation). This risk is maintained after controlling for age, gender, left ventricular ejection fraction, heart failure symptoms and medication use.
2. Patients with a normal heart rate response to regadenoson have a low rate of events (death or appropriate cardiac defibrillation) despite meeting current indications for having an ICD.

Background:

In patients with left ventricular systolic dysfunction and in those with a history of sudden cardiac death, an ICD reduces mortality.¹⁻³ However, not all patients with an ICD receive appropriate therapy from it (In a large study, only one third of patients received appropriate therapy from an ICD over the first 3 years of follow-up)⁴, and inappropriate ICD shocks are common and are associated with worse quality of life and increased mortality.⁵ Furthermore, ICDs are expensive (the procedure costs ~\$35,000) and place a toll on the health care system. Establishing a better predictor of risk of sudden cardiac death and of response to ICD is desirable.

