1. Prior to the implantation of a clinically indicated ICD, the heart rate response to regadenoson will be assessed. Regadenoson will be administered intravenously as a fixed intravenous bolus dose of 400 µg followed by a 5 mL saline flush. Medications (including beta-blockers) will be withheld on the morning of the test. The heart rate and blood pressure will be measured at baseline and every minute after regadenoson bolus for at least 5 minutes and until the heart rate and blood pressure are clearly returning towards baseline. The peak heart rate will be defined as the maximum achieved heart rate after regadenoson injection. The peak blood pressure will be defined as the blood pressure when the systolic component is at a minimum during the test. The heart rate and blood pressure response will be calculated for each patient as the maximum percent change from baseline.^{7, 8} A heart rate response in the lowest tertile will be defined as blunted. A heart rate response in the highest tertile will be defined as normal. Secondary analyses will be performed with the heart rate response as a continuous variable and using the following cut-offs, <20% (blunted), ≥40% (normal).^{10, 11}
2. An ICD will be placed for clinical indications using standard techniques.

Follow-up: 2-years from the time of ICD implantation.

Duration of study: 4 years

Endpoints:

1. Primary Endpoint: Sudden cardiac death
2. Secondary Endpoints
 - a. All-cause death
 - b. First appropriate ICD therapy
 - c. All-cause death or first appropriate ICD therapy
 - d. Inappropriate ICD therapy

Patients will be followed up at 6 months intervals with ICD interrogation. ICD therapy (shocks or anti-tachycardia pacing) will be determined as appropriate or inappropriate by an experienced clinical electrophysiologist ([name]) after review of the intra-cardiac electrograms. If patient fails to show up at their scheduled appointment, patients or their designated relatives will be contacted to verify their status. In case of death, relatives will verify circumstances of death.

SCD will be strictly defined as death within 1 hour of symptom onset, or an unobserved death in which the patient was seen and known to be doing well within 24 hours of death. Survivors of aborted SCD, resuscitated cardiac arrest, and those receiving appropriate ICD therapy will also be considered to have experienced SCD and will be included in the primary end point.^{13, 14}

Sample Size:

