In a recent study from our group, patients with ICD implanted for primary prevention at our center experienced an event rate of death or first appropriate ICD therapy ~ 20% over first 2 years.¹⁵ In our recent study on the heart rate response to regadenoson, patients in the lowest heart response tertile experienced a 4-fold increased risk of death compared to those in the highest tertile.¹¹ We believe that is a conservative estimate of risk for this study since the heart rate response should be a better predictor of sudden cardiac death than overall mortality. A sample size of 126 patients will provide a 90% power to detect a 4-fold increase in risk of the primary outcome for patients in the lowest compared to the highest tertile of the heart rate response to regadenoson (40% vs. 10% over 2 years) at a preset P value of 0.05. We plan for a sample size of 150 to account for any dropouts and or loss of follow-up.

Statistical Plan:

All statistical analyses will be carried out using SPSS version 17 for Windows (SPSS Inc., Chicago, Illinois). We will collect data on patient demographics (age, gender, race, education), patient characteristics (height, weight), co-morbidities (history of myocardial infarction, diabetes mellitus, hypertension, dyslipidemia, atrial fibrillation, stroke), prior cardiovascular procedures (percutaneous coronary intervention or coronary artery bypass grafting), habits (tobacco use), symptoms (NYHA classification), medication intake (aspirin, beta-blocker, calcium channel blocker, angiotensin converting enzyme inhibitor (ACE-I), angiotensin receptor blocker (ARB), aldosterone antagonist, loop diuretic, statin, insulin), electrocardiographic characteristics (left bundle branch block, right bundle branch block, QRS, QT, PR) and laboratory results (serum creatinine, electrolytes, brain natriuretic peptide).

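### The 90% power figure is computed correctly, but its inputs do not describe the primary endpoint as defined under Endpoints, and Amendment 3 has no power statement

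*Combined protocol and SAP*

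**What the plan says.** All references are to the combined protocol and SAP.

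- **Sample Size.** The one event rate comes from an earlier cohort at the centre, whose primary-prevention ICD patients "experienced an event rate of death or first appropriate ICD therapy ~ 20% over first 2 years". The effect size is a 4-fold risk of death, lowest vs highest tertile of heart rate response, from the group's earlier regadenoson study. The section then states: "A sample size of 126 patients will provide a 90% power to detect a 4-fold increase in risk of the primary outcome", at 40% vs 10% over 2 years. The target is raised to 150 for losses. Of the 4-fold ratio it says "We believe that is a conservative estimate of risk for this study", because heart rate response should predict sudden cardiac death (SCD) better than overall mortality.
- **Endpoints.** The primary endpoint is SCD: "SCD will be strictly defined as death within 1 hour of symptom onset, or an unobserved death" in a patient known to be well within the previous 24 hours. Aborted SCD and resuscitated arrest count too, and "those receiving appropriate ICD therapy will also be considered to have experienced SCD and will be included in the primary end point". Secondary endpoint c is "All-cause death or first appropriate ICD therapy".
- **Hypotheses, item 1.** Patients with a blunted response "are at higher risk of sudden cardiac death (death or appropriate cardiac defibrillation"), so SCD is explained there as a composite that includes any death. Hypothesis 2 uses the same composite.
- **Statistical Plan.** Three groups of 50, two-sided 0.05, Kaplan-Meier and log-rank, Cox hazard ratios with 95% confidence intervals, and censoring at 2 years from evaluation.
- **Amendments, item 3.** Follow-up and sample size are shortened; follow-up now runs from the regadenoson MPI to the end of the study. No number of patients, follow-up length, end date or power is given.

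**The concern.** A power statement holds only for the endpoint and design that its inputs describe. Here the planning rate is the rate of a secondary endpoint, and the power is claimed for the primary one. The primary endpoint itself has two definitions. Under Endpoints, a non-sudden death in a patient with no earlier primary event does not count; under Hypotheses, it does. The planning rate fits only the Hypotheses wording, and under that wording the primary endpoint nearly duplicates secondary endpoint c.

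Separately, every planning figure in the document (126, 150, 50 per group, 2 years) describes the study before Amendment 3. The point is not that the amendment list differs from the body. The list is the only description of the amended design, and no power accompanies it.

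At stake is how a non-significant result is read. A reader will credit the study with 90% power for SCD, a figure the plan supports neither for the endpoint as defined under Endpoints nor for the amended size and follow-up.

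**Working it through.** **Method.** Two-proportion comparison of lowest vs highest tertile, two-sided 0.05, pooled variance under the null, no continuity correction, n = N/3 per tertile, no dropout:

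power = Φ{ [ |p1 − p2|·√n − 1.96·√(2·p̄(1 − p̄)) ] / √( p1(1 − p1) + p2(1 − p2) ) }, with p̄ = (p1 + p2)/2.

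**1. The plan's own figure.** Inputs from Sample Size: p1 = 0.40, p2 = 0.10, N = 126, so n = 42 and p̄ = 0.25.

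- Numerator: 0.30 × 6.481 − 1.96 × 0.612 = 1.944 − 1.200 = 0.744.
- Denominator: √(0.24 + 0.09) = 0.574.
- Power = Φ(1.295) = 90.2%. The stated 90% reproduces.
- At N = 150 (n = 50) the same inputs give 94.6%.

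**2. Do 40% and 10% fit a 20% overall rate?** With equal tertiles, (40 + m + 10)/3 = 20 requires m = 10%. The middle tertile would have to carry the same risk as the highest-response tertile. Assume instead a graded pattern, with the middle tertile at twice the highest tertile's risk x and the lowest at 4x:

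- (x + 2x + 4x)/3 = 0.20, so x = 0.60/7 = 8.6% and 4x = 34.3%.
- Power: 83% at N = 126 and 89% at N = 150.

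This step applies even if the Hypotheses definition governs.

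**3. The Endpoints definition.** The documents give no rate for it and no share of non-sudden deaths. The shares below are assumptions, applied to 40% and 10%.

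| Share of composite events that qualify | Ratio | Rates | N = 126 | N = 150 |
|---|---|---|---|---|
| 90% | 4 | 36% vs 9% | 86% | 91% |
| 80% | 4 | 32% vs 8% | 80% | 86% |
| 80% | 5 | 33.3% vs 6.7% | 88% | not needed here |
| 80% | 6 | 34.3% vs 5.7% | 92% | not needed here |

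The last two rows keep the summed risk of the two outer tertiles at 40% (32 + 8) and raise the ratio in the direction the plan argues for.

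**4. Amendment 3.** The reduced N is not stated, so these values are illustrations. With 40% vs 10% and full two-year follow-up kept:

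- N = 99 (n = 33): 82%.
- N = 75 (n = 25): 70%.

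Follow-up shorter than two years would lower both further.

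**The case against.** **The ratio may exceed 4.** The plan argues that 4-fold is conservative for SCD, and power depends on the ratio as well as the rate. This stands. With an 80% share, a ratio of 5 brings power at 126 patients back to 88%, and a ratio of 6 to 92%. The Endpoints definition also counts all appropriate ICD therapy, including anti-tachycardia pacing, and some unobserved deaths, so the events lost may be few. A reader might infer that the study is underpowered for SCD; the documents do not support that. Equally, the plan gives no rate from which 90% follows.

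**The planning rate matches Hypothesis 1.** True, but that wording contradicts the strict definition under Endpoints, and it leaves the middle-tertile problem in place.

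**Amendment 3 does define follow-up.** It gives a rule, from MPI to end of study. A reader might infer that no follow-up is specified; that goes too far. What is missing is a length or an end date. A reader might also infer that follow-up to end of study removes the two-year censoring and then put a figure on the change in power. That would need an accrual pattern the documents do not give, and an amendment meant to shorten follow-up does not readily read as lifting a maximum. Whether the censoring still applies needs only a sentence.

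**The test is a log-rank test, not a comparison of proportions.** The plan's figure reproduces exactly with the two-proportion formula, so the same yardstick is used throughout. By simulation, the plan's inputs give about 91% for a pairwise log-rank test at 126 patients, and about 88% for a three-group test with an assumed 20% middle tertile. The choice of test shifts the figures modestly and does not settle the endpoint question.

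**Interval estimates are planned.** Hazard ratios with 95% confidence intervals are the better guide to a null result, and this limits the harm. It does not correct the stated figure.

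**Conclusion.** The power statement is wrong as written in what it is attached to, not in its arithmetic. Three things are certain from the text: the planning rate is that of secondary endpoint c; the Hypotheses and Endpoints sections define the primary endpoint differently; and no power is given for the sample size and follow-up after Amendment 3.

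The size is conditional. Under the Hypotheses definition, 20% overall with a 4-fold ratio and an assumed graded middle tertile gives 83% at 126 patients and 89% at 150. Under the Endpoints definition, 90% is neither shown nor excluded: 80% to 86% at 126 patients and 86% to 91% at 150 for assumed shares of 80% to 90% at ratio 4, and higher if the ratio exceeds 4. For the amended design, any smaller N or shorter follow-up lowers power with the other inputs fixed, but by how much cannot be computed from the documents. Amendments 1 and 2 also admit generator exchanges and patients with an ICD already in place, so the 20% rate may not carry over, in an unknown direction.

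Severity is minor to moderate.

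**What to change.** 1. Reconcile Hypotheses and Endpoints so that one definition of the primary endpoint governs. If it is the Hypotheses wording, also resolve the overlap with secondary endpoint c.
2. Keep the existing calculation as the historical rationale, and add beside Amendment 3: the amended number of patients; the expected follow-up, with its length or the end date; a planning rate, or a stated range, for the governing endpoint; tertile rates consistent with that overall rate; and the resulting power, or the smallest detectable hazard ratio, for lowest vs highest tertile.
3. Take the rate from planning data, for example the earlier ICD cohort with events counted by the governing definition. Do not use this study's observed effect. If the statement is written after the amendment took effect, say so.
4. Update the figure of 50 patients per group in the Statistical Plan, and state whether the two-year censoring there still applies.

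The cost is wording and a short recalculation. No new patients, data, endpoint or test is needed. The one downside is that the stated power may come out less favourable.

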The population will be divided into 3 groups with 50 patients in each group based on tertiles of the heart rate response on regadenoson. Continuous variables will be presented as mean \pm SD and discrete variables as frequencies and percentages. The chi-square test or an analysis of variance (ANOVA) will be used for the comparison of categorical variables. Continuous variables will be compared using the unpaired student t test or the Mann-Whitney U test, as appropriate. In order to determine the predictors of the HRR to regadenoson, a linear regression model will be constructed with the HRR as the dependent variable and all the characteristics that are associated with the HRR ($p < 0.2$) as independent variables. An estimation of the effect of each of the variables on the HRR will be determined based on the coefficient of the variable in the regression equation. Follow-up time will be calculated from the time of evaluation to sudden cardiac death or to end of follow-up censored at 2 years from time of evaluation. Event-free survival curves will be constructed using the product-limit method (Kaplan-Meier) and differences among survival curves will be estimated by the log-rank test. Cox proportional hazard analysis will be used to estimate unadjusted and age, gender and LVEF adjusted (multivariate) risks for sudden cardiac death. We will introduce interaction terms to test for interaction between HRR and the different variables in the model. Estimated risks will be reported as hazard ratios (HR) with correspondent 95% confidence intervals (CI). All tests will be 2-tailed, and a p value of < 0.05 will be considered statistically significant.

Amendments

During the conduction of the trial, the following amendment were introduced:

1. The original protocol enrolled patients with a clinical indication for an implanted cardiac defibrillator (ICD) for primary prevention of sudden cardiac death. We amended the protocol to enroll patients who are undergoing an ICD implantation or a generator exchange for clinical indications.

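### Minor: if the Endpoints definition governs, non-sudden death competes with the primary endpoint, and Kaplan-Meier curves that censor it would modestly overstate the probability of sudden cardiac death (SCD)

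*Combined protocol and SAP*

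**What the plan says.** The Endpoints section makes SCD the primary endpoint and confines its fatal part to sudden deaths: "SCD will be strictly defined as death within 1 hour of symptom onset", or an unwitnessed death in a patient known to have been well in the preceding 24 hours. Aborted SCD, resuscitated arrest and appropriate ICD therapy also count. All-cause death is a separate secondary endpoint, as is "All-cause death or first appropriate ICD therapy". Information on the manner of death is gathered: "In case of death, relatives will verify circumstances of death".

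Hypothesis 1 describes the outcome differently: "higher risk of sudden cardiac death (death or appropriate cardiac defibrillation", which takes in any death. Hypothesis 2 likewise expects a "low rate of events (death or appropriate cardiac defibrillation) despite meeting current indications for having an ICD".

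The Statistical Plan gives the time axis as "Follow-up time will be calculated from the time of evaluation to sudden cardiac death or to end of follow-up censored at 2 years". It continues: "Event-free survival curves will be constructed using the product-limit method (Kaplan-Meier". The curves are compared by log-rank test, Cox models follow, and "Estimated risks will be reported as hazard ratios (HR" with confidence intervals. Neither non-sudden death, competing events nor cumulative incidence is mentioned. Amendment 3 changes follow-up to run from the regadenoson imaging to the end of the study.

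**The concern.** Under the Endpoints definition, a patient who dies non-suddenly before any primary event can no longer have one. Censoring that patient treats the death like a withdrawal after which SCD could still occur. One minus the Kaplan-Meier estimate then answers what would happen if nobody died of other causes, and it exceeds the proportion who actually have SCD.

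The study wants to use heart rate response to judge who is likely to benefit from an ICD. That is partly a question of absolute risk, and the curves are the natural place to look for it. The excess is larger where event rates are higher, so it falls mainly on the blunted tertile. Also, because the plan does not name these deaths, two analysts could code the same death differently.

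**Working it through.** **Inputs.** From Sample Size: 40% against 10% over 2 years (lowest against highest tertile), 90% power, alpha 0.05, 126 patients, and a centre rate of about 20% over 2 years for death or first appropriate therapy. From the Statistical Plan: two-sided tests and 50 patients per tertile. Assumed, because the documents give no figure: the rate of non-sudden death, and constant hazards.

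**The plan's own figure.** For two proportions with pooled variance, n = [1.960·√(2·0.25·0.75) + 1.282·√(0.4·0.6 + 0.1·0.9)]² / 0.30² = 41.7, so 42 per tertile and 3 × 42 = 126, as stated. No censoring rule enters this calculation.

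**Formulas.** Let λ be the yearly SCD hazard and μ the yearly hazard of non-sudden death.
- Deaths censored: 1−KM(t) = 1 − exp(−λt).
- Cumulative incidence: CIF(t) = λ/(λ+μ) × [1 − exp(−(λ+μ)t)].

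**Case 1: 40%/10% is the composite of SCD or other death.** Total hazards are L = −ln(0.6)/2 = 0.2554 (blunted) and −ln(0.9)/2 = 0.0527 (normal) per year, ratio 4.85. If the middle tertile is assumed equal to the normal one, the average is (40+10+10)/3 = 20%, which agrees with the centre rate. With non-sudden share s, λ = (1−s)L and μ = sL. At 2 years:

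| s | Blunted 1−KM | Blunted CIF | Excess (points) | Normal 1−KM | Normal CIF | Excess (points) |
|---|---|---|---|---|---|---|
| 10% | 36.86% | 36.00% | 0.86 | 9.05% | 9.00% | 0.05 |
| 25% | 31.83% | 30.00% | 1.83 | 7.60% | 7.50% | 0.10 |
| 50% | 22.54% | 20.00% | 2.54 | 5.13% | 5.00% | 0.13 |

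These shares mean 2, 5 or 10 non-sudden first deaths per 50 blunted patients (4%, 10%, 20%) and 0.5, 1.25 or 2.5 per 50 normal patients.

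**Case 2: 40% reflects the SCD hazard alone, and non-sudden death is added.** For the blunted tertile λ = 0.2554 and μ = −ln(1−q)/2. Then 1−KM is 40% throughout. With q = 5%, 10% or 20%, CIF is 39.1%, 38.1% or 36.2%, an excess of 0.9, 1.9 or 3.8 points.

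**Shorter follow-up.** Amendment 3 gives no new length, so 1 year serves as an illustration. In case 1 the blunted excess falls to 0.25, 0.53 or 0.72 points, and the normal excess is at most 0.03.

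**The literal alternative.** If a dead patient stayed in the risk set to 2 years, 1−KM would equal the cumulative incidence (apart from other censoring). A simulation with s = 25% and a 40% composite gives 0.300 under this rule and 0.319 with deaths censored. The hazard ratio would change instead. With risk sets 1 − CIF(t) and two equal groups, 4.85 becomes 4.74, 4.58 or 4.36 in case 1. It can also rise: with SCD at the 40%/10% hazards and non-sudden death of 5% (blunted) and 10% (normal), it is 4.96.

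**Scale.** The 95% sampling half-width with 50 patients, 1.96·√(p(1−p)/50), is 13.4, 12.9 or 11.6 points at the three blunted 1−KM values in case 1.

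**The case against.** The strongest reply is that the plan already works. A patient's follow-up ordinarily ends at death, so the stated time axis contains a usable rule, and under it log-rank and Cox are proper cause-specific analyses. The plan reports risk as hazard ratios and nowhere undertakes to quote one minus Kaplan-Meier as a probability. Non-sudden deaths will be visible through the secondary endpoints. If the wording in the Hypotheses governs, no death competes at all. All of this stands, and it is why the point is minor.

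The size can also be challenged, because the shares are assumed and the meaning of 40% is uncertain: Sample Size calls it the primary outcome. If 40% were the cumulative incidence of SCD itself and 5%, 10% or 20% died non-suddenly first, 1−KM = 1 − (1−T)^(0.40/T), with T the sum of the two, is 41.2%, 42.6% or 45.7%. The excess would then be 1.2, 2.6 or 5.7 points. So small is a fair description for most of the range, not a guarantee.

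A reader might infer more than the documents support:
- **That the missing rule by itself biases the curve.** It does so only if deaths are censored when they occur.
- **That the planned hazard ratio or log-rank test is invalid.** On the ordinary reading neither is.
- **That the normal tertile's low event rate is in doubt.** Hypothesis 2 counts death as an event, and the normal-tertile excess is at most 0.13 points in case 1.
- **That 126 is wrong.** It reproduces and does not depend on the censoring rule.

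**Conclusion.** The point holds as a cheap improvement, on two conditions: the Endpoints definition governs, and non-sudden deaths are censored when they occur. The Kaplan-Meier SCD curve, if read as a probability, is then too high by 0.9 to 2.5 points in the blunted tertile when 40% is the composite, or by 0.9 to 3.8 points when 40% reflects the SCD hazard alone. With shorter follow-up the excess is smaller. All these sizes rest on assumed non-sudden death rates and constant hazards.

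The case 1 excess lies well inside the sampling error for 50 patients, and amendment 3's smaller sample would widen that error at the same rates. The excess does, however, always run in the same direction. On the less likely literal reading the curve is sound but the hazard ratio is no longer cause-specific. No conclusion on either hypothesis is shown to change.

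**What to change.** First reconcile the primary event between Hypotheses (any death or appropriate defibrillation) and Endpoints (sudden death, aborted SCD, resuscitated arrest or appropriate therapy). If the Hypotheses wording stands, the curve needs no change.

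If the Endpoints wording stands, amend the Statistical Plan as follows:
- State that follow-up ends at the earliest of SCD, other death, loss to follow-up or end of follow-up, with the 2-year limit reconciled with amendment 3.
- Replace the Kaplan-Meier SCD curves with cumulative incidence of SCD by tertile, treating non-sudden death as a competing event.
- Label the log-rank and Cox results cause-specific.
- Show non-sudden deaths by tertile and secondary endpoint c alongside.

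The cost is one clause, one curve definition and slightly more analysis work, possibly in software other than SPSS 17. Deaths and their circumstances are already collected, so no new data are needed.

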Adenosine and regadenoson are routinely used as pharmacological stress agents to induce coronary hyperemia for myocardial perfusion imaging (MPI) in lieu of exercise. The increase in heart rate seen during adenosine infusion has previously been attributed to its vasodilatory effect on the systemic circulation and has thus generated little interest. Recently, it was recognized that this rise in heart rate is related to a direct stimulation of the sympathetic nervous system by adenosine therefore allowing for a novel simple method for the evaluation of autonomic function.⁶ Using data from the ADenoscan Versus RegAdenoson Comparative Evaluation for Myocardial Perfusion Imaging (ADVANCE MPI 1 and 2) Trials, we demonstrated that patients with diabetes mellitus have a blunted heart rate response to adenosine presumably due to cardiac autonomic dysfunction.⁷ Furthermore, the heart rate response associated with multiple risk factors of sudden cardiac death.^{7, 8} Since cardiac autonomic dysfunction has been linked to increased

cardiovascular risk,⁹ we postulated that the heart rate response may carry useful prognostic information. Recently we showed that a blunted heart rate response to adenosine is associated with increased mortality in the overall population and that it assisted in the risk stratification of patients at high risk (such as those with diabetes mellitus or chronic kidney disease) when added to traditional MPI findings.¹⁰ In a Cox regression model, a blunted heart rate response was the strongest predictor of mortality and provided additional prognostic data to MPI after controlling for age, gender, race, history of myocardial infarction, diabetes mellitus, chronic kidney disease and beta-blocker use. We also demonstrated that a decreasing heart rate response to regadenoson is associated with stepwise increase in mortality.¹¹ In a Cox proportional model for mortality that adjusted for age, gender, diabetes mellitus, renal disease and MPI findings, heart rate response to regadenoson in the lowest quartile was independently associated with 5-fold increase in mortality compared to the highest quartile. Patients with a normal heart rate response had a relatively low annualized total mortality despite the presence of risk factors.

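### The Statistical Plan does not carry through hypothesis 1 or the powered contrast: its Cox model omits two covariate groups, its log-rank test is not tied to lowest versus highest tertile, and two descriptive test rules do not fit.

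*Combined protocol and SAP*

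**What the plan says.** - **Hypotheses.** Hypothesis 1 states that patients with a blunted response are at higher risk, and adds: "This risk is maintained after controlling for age, gender, left ventricular ejection fraction, heart failure symptoms and medication use".
- **Protocol, item 1.** The groups are labelled: "A heart rate response in the lowest tertile will be defined as blunted" and "A heart rate response in the highest tertile will be defined as normal". Other codings are set below this: "Secondary analyses will be performed with the heart rate response as a continuous variable and using the following cut-offs", with limits at 20% and 40%.
- **Sample Size.** 126 patients give 90% power to detect 40% against 10% over 2 years "for patients in the lowest compared to the highest tertile of the heart rate response to regadenoson". The plan is to enrol 150 to allow for losses. The background rate comes from the centre's own primary-prevention patients, who "experienced an event rate of death or first appropriate ICD therapy ~ 20% over first 2 years".
- **Statistical Plan.** The population is split into three tertile groups of 50. Kaplan-Meier curves are drawn and "differences among survival curves will be estimated by the log-rank test". Cox models give risks for sudden cardiac death, unadjusted and adjusted for age, gender and LVEF. None of these results is called primary. For other comparisons, chi-square or ANOVA is assigned to categorical variables, and the t test or Mann-Whitney test to continuous variables. NYHA class and nine medication types are among the data to be collected.
- **Amendments, item 3.** Follow-up and sample size are reduced, with no new number given.

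**The concern.** Three statements in the Statistical Plan do not match what earlier sections set up.

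First, the adjusted model leaves out two of the five covariate groups that hypothesis 1 names. Objective 1 is a claim of independent prediction. Symptom class and drugs such as beta-blockers could plausibly relate to both heart rate response and outcome. A significant hazard ratio from the three-covariate model would leave the hypothesis as worded untested.

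Second, the study is powered on one pair of tertiles, but the log-rank sentence reads most naturally as one test across three curves (2 degrees of freedom). Log-rank, unadjusted Cox and adjusted Cox are left without an order. If they disagree, the plan does not say what is concluded. The power of a three-curve test depends on the middle-tertile rate, which the plan does not give. The Background reports, for mortality in an earlier study, that "a decreasing heart rate response to regadenoson is associated with stepwise increase in mortality", so an intermediate rate is plausible.

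Third, two descriptive rules do not fit. ANOVA is not a test for categorical variables. The t test and Mann-Whitney test compare two groups, not three.

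**Working it through.** **1. Covariates side by side.**
- Hypothesis 1: age, gender, LVEF, heart failure symptoms, medication use.
- Adjusted Cox model: age, gender, LVEF.
- Missing: heart failure symptoms and medication use, both collected.

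Events available, if the roughly 20% two-year rate (quoted for death or first appropriate ICD therapy) is assumed to hold for the primary endpoint: 0.20 × 126 = 25 and 0.20 × 150 = 30.
- Tertile (2 df) + age + gender + LVEF = 5 df: 25/5 = 5 to 30/5 = 6 events per parameter.
- Adding NYHA class (I–III, 2 df) and one drug, such as beta-blocker (1 df) = 8 df: 25/8 = 3.1 to 30/8 = 3.8.
- Adding NYHA class and all nine drugs = 5 + 2 + 9 = 16 df: 25/16 = 1.6 to 30/16 = 1.9.

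**2. The plan's sample size.** Inputs: 40% and 10%, two-sided 0.05, power 90%, pooled rate 0.25.

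n per tertile = [1.96 × √(2 × 0.25 × 0.75) + 1.2816 × √(0.40 × 0.60 + 0.10 × 0.90)]² / 0.30² = (1.200 + 0.736)² / 0.09 = 41.7, rounded up to 42.

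3 × 42 = 126, as stated. Power is 90.2% at 42 per tertile and 94.6% at 50. The figure is correct, and it belongs to a comparison of the two outer tertiles.

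**3. Middle-tertile rate.** It is not stated. With about 20% overall, (40 + m + 10)/3 = 20 gives m = 10%. The range 10–40% is used below as an assumption.

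**4. Power of the two log-rank readings.** Simulation with exponential times, hazard −ln(1 − p)/2 per year, censoring at 2 years, two-sided 0.05, and 10,000 runs per row (Monte Carlo error about 0.3 points). Outer tertiles 40% and 10%.

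| Assumed middle rate | Three curves, 42 per tertile | Lowest vs highest, 42 per tertile | Three curves, 50 per tertile |
|---|---|---|---|
| 10% | 95.0% | 91.3% | 98.1% |
| 15% | 90.3% | 91.3% | 94.4% |
| 20% | 85.7% | 91.5% | 91.8% |
| 25% | 84.1% | 91.1% | 90.5% |
| 30% | 85.9% | 91.5% | 91.6% |
| 35% | 89.1% | 91.5% | 94.5% |
| 40% | 92.7% | 91.4% | 96.8% |

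A separate set of 8,000 runs gave 86.5%, 84.8% and 85.6% for three curves at middle rates of 20%, 25% and 30%, so about 84–87% in that range. Lowest versus highest at 50 per tertile is 95–96% throughout. The 42-per-tertile columns describe the 126 patients left after planned losses; 50 per tertile means no losses from 150.

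**5. Descriptive tests.** Chi-square is valid for a categorical variable across three tertiles, so the fault in that rule is ANOVA (variable type). For continuous variables, two-sample tests would serve blunted versus normal but not three tertiles.

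**The case against.** The protocol and SAP are one document. The Protocol section labels lowest as blunted and highest as normal and makes other codings secondary, and the Sample Size section ties the primary outcome to that pair. The Statistical Plan need not repeat this. That largely stands: the intended contrast can be inferred. What cannot be inferred is whether the log-rank test is that pair or all three curves, and which result decides.

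Three stronger readings are tempting and are not supported.
- *The trial is underpowered.* The only middle rate that the plan's figures imply, 10%, gives the three-curve test more power than the pair. The fall to 84–87% needs assumed rates of 20–30% and only 126 evaluable patients. The stepwise relation cited in the Background concerns mortality in an earlier study, not this endpoint.
- *Type I error is inflated.* It would be 7–8% only if either log-rank test may decide. No section says so. A fixed order, three curves first and then the pair, would keep it at or below 5%.
- *The Cox hazard ratio is undetermined.* A reference tertile should be stated, but pooling tertiles or fitting a per-step trend is not proposed anywhere. This is missing detail.

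On the descriptive rules, another reading is possible: heart rate response compared between two levels of a characteristic (t test) or across several (ANOVA), as the p < 0.2 screen might use. The text does not say this, so the wording still needs correction.

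The short covariate list may be deliberate, given few events. That is a fair reason to narrow hypothesis 1, but as written the two do not agree.

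**Conclusion.** The concern holds as a minor one that needs clarification. The firmest part is the covariate mismatch: the adjusted model as planned cannot support hypothesis 1 as worded. The sample size is correct, but for a contrast that the log-rank sentence does not name. The cost of reading that sentence as a three-curve test runs from a gain of about 4 points (middle rate 10%) to a loss of about 7 points (middle rate 25%) at 126 evaluable patients. With 50 per tertile, every reading keeps about 90% or more. The descriptive rules contain one variable-type error and one set of tests that does not fit three groups.

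The power figures assume 40% and 10% in the outer tertiles, constant hazards, full 2-year follow-up and the stated range of middle rates. They apply to the original design only. Power after amendment 3 cannot be computed, because no new sample size is given.

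**What to change.** Amend the Statistical Plan as follows.

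1. **Primary test.** Two-sided 1-df log-rank of lowest versus highest tertile on the primary endpoint, at 0.05. Three-curve, trend, continuous and cut-off analyses are supportive.
2. **Cox model.** Tertile as a three-level factor with the highest tertile as reference, reported unadjusted and adjusted. The claim of an independent predictor requires the adjusted lowest-versus-highest hazard ratio to be significant. If the log-rank is significant and the adjusted hazard ratio is not, report an association, not independence.
3. **Covariates.** Either add a short list to age, gender and LVEF (for example NYHA class and beta-blocker use), or narrow hypothesis 1 to the three covariates now planned.
4. **Descriptive tests across tertiles.** Chi-square or Fisher for categorical variables; ANOVA or Kruskal-Wallis for continuous variables. Name the test behind the p < 0.2 screen.
5. **Timing.** If outcomes have already been seen, say that these choices were made afterwards.

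The cost is a few sentences, with no new data and no change to the original sample size. There are two downsides. The middle tertile is left out of the primary p value, with slightly lower power (91% against 95% at 42 per tertile) if its risk equals that of the highest tertile. Also, with about 25–30 events on the original design, the adjusted model has few events per parameter (about 3 to 4 with the example list), so the list must stay short.
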